5.4.10 Response Assessment

Response assessment will be performed in conjunction with the post dose disease assessments ie, every 8 weeks for the first 3 assessments, then every 12 weeks thereafter, as well as at the time of suspected clinical progression, as described in Schedule of Assessments [REDACTED]

Response assessment will follow the modified Lugano Classification Revised Staging System for malignant lymphoma ([Cheson, 2014](#)) for subjects with PTCL (Cohorts A and B) and the Olsen Criteria ([Olsen, 2011](#)) for subjects with TMF (Cohort C) [REDACTED]

The modified Lugano Classification refers to the protocol's separate use of PET-CT based response criteria from CT-based response criteria from the Lugano Classification to guide clinical decisions and assessment of overall response. The CT-based overall response will be one of the secondary endpoints.

For Cohort C (TMF), the Olsen Criteria determines the global response (GR) based on the following:

- skin assessment by the modified Severity Weighted Assessment Tool (mSWAT) and Composite Assessment of Index Lesions Severity (CAILS)

- lymph node assessment by CT (or MRI)
- visceral disease assessment by CT (or MRI)
- blood assessment by flow cytometry (ie, CD4-positive/CD7-negative and CD4-positive/CD26-negative subsets)

[REDACTED]

Assessments will be performed both locally and centrally, and all imaging scans (PET-CT for Cohorts A and B, CT or MRI for Cohort C) will be collected for independent review. Treatment decisions should be based on the local disease assessment.

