8.6.2 Analysis of efficacy endpoints

The primary endpoint is based on the IRC PET-CT-based metabolic responses. Secondary endpoints are based

Final Analysis Statistical Analysis Plan (SAP)

on IRC CT based radiologic responses and on Investigator (CT or FDG-PET (=PET-CT)) responses.

Overall response

Within each visit an overall response will be determined by the IRC and Investigator on CT-based radiographic responses and FDG-PET (=PET-CT) based metabolic responses separately utilizing the modified Lugano Classification revised staging system for malignant lymphoma (Cheson 2014) for Cohorts A and B (PTCL) and the Olsen Criteria (Olsen 2011) for Cohort C (TMF).

Subjects who cannot be evaluated for response will be categorized as not evaluable (NE).

Best overall response (BOR)

The best overall response is the best response recorded from the start of the treatment until disease progression/recurrence or death. All disease responses obtained after progressive disease, start of new anti-cancer therapy or a transplant are excluded from the best overall response. Best is defined as the first response when all a subject's response assessments are sorted by complete response/complete radiologic response/complete metabolic response (CR), partial response/partial remission/partial metabolic response (PR), stable disease/no metabolic response (SD), pseudoprogression, progressive disease/progressive metabolic disease (PD), not evaluable (NE).

The subject's best response assignment will depend on the achievement of the measurement criteria (confirmation is not required). BOR will be summarized using a frequency table by cohort. For Cohorts A and B, BOR is derived for radiographic (using only CT-based responses) and metabolic responses (using only FDG-PET (=PET-CT) based responses) separately.

Overall response rate (ORR)

ORR is calculated as the proportion of subjects with a CR or PR. Subjects without at least one post-baseline response assessment will be treated as non-responders.

ORR and Pearson-Clopper 95% confidence interval (CI) will be displayed separately for CT-based response and FDG-PET (=PET-CT) based response. CR and PR rates and their Pearson-Clopper 95% CI will be also displayed separately.

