As the study design is based on a Simon's two stage design (See Section 5), an exact binomial test will be performed to analysed the ORR of the Cohorts A and C at the final analysis only. The one-sided p-value will be displayed. The tested hypotheses are as follows for each cohort:

Cohort A: $H_0: p \leq 0.25$

$H_1: p > 0.25$

Cohort C: $H_0: p \leq 0.05$

$H_1: p > 0.05$

For all response assessments, swimmer plots will be presented. All response assessments will be also listed.

The above analyses (overall response, BOR and ORR) will be performed for each cohort and for:

Response evaluator	Population of analysis	Analysis order
IRC	FAS	Primary analysis
IRC	FAS with at least one post-baseline efficacy assessment	Sensitivity analysis, if deemed necessary (based on the number of subjects included in that population after the Classification Meeting)
IRC	COVID analysis set	Sensitivity analysis, if deemed necessary (based on the number of subjects included in that population after the Classification Meeting)
IRC	PP set	Sensitivity analysis, if deemed necessary (based on the number of subjects included in that population after the Classification Meeting)
Investigator	FAS	Secondary analysis
██████████	████████████████████	██ ██ ██

These analyses will be also repeated for the subgroups defined in Section 8.8.5 for the FAS.

Duration of response (DOR)

The DOR is defined as time from first assessment of PR or CR to the first assessment of progressive disease or death due to any cause separately for IRC and Investigator using respectively only IRC or Investigator assessments. DOR will be censored for IRC assessments using Table 1 and Investigator assessments using Table 3 when analyses are performed on FAS or PP set. The Table 2 and Table 4 will be used when the analyses are performed on the COVID analysis set:

Final Analysis Statistical Analysis Plan (SAP)

Table 1: Independent Review Committee Assessments (IRC) Censoring Rules

Event	Event or censored date	Event or censored
Progression (as determined by IRC)	Date of progression (as determined by IRC)	Event
Death due to any cause	Date of death	Event
PD (as determined by IRC) or death after 1 missed assessment (ie, ≥ 59 days between 2 assessments until Cycle 4 and ≥ 87 days from Cycle 5)	Date of PD (as determined by IRC) or death	Event

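### SAP 8.6.2 ranks pseudoprogression above PD in best overall response and, in the visible text, does not say how BOR and DOR are handled when the next evaluable scan shows PD

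*SAP*

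**What the plan says.** SAP 8.6.2 sets an overall response at each visit, separately for IRC and Investigator and for CT and PET-CT. BOR is the top entry after a subject's responses are sorted. CR and PR come first, and the rest of the order is "stable disease/no metabolic response (SD), pseudoprogression, progressive disease/progressive metabolic disease (PD), not evaluable (NE". The only responses removed from the sort are late ones: "All disease responses obtained after progressive disease, start of new anti-cancer therapy or a transplant are excluded from the best overall response". Of confirmation of a best response, the SAP says "confirmation is not required". For the response rate, "ORR is calculated as the proportion of subjects with a CR or PR".

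DOR in the same section is the "time from first assessment of PR or CR to the first assessment of progressive disease or death due to any cause". In Table 1 the event date for a progressor is the "Date of progression (as determined by IRC"), and Table 3 has the matching row for the Investigator. Neither table has a row or note for pseudoprogression.

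Protocol 5.4.10 explains modified Lugano as the "separate use of PET-CT based response criteria from CT-based response criteria from the Lugano Classification". Response is assessed "every 8 weeks for the first 3 assessments, then every 12 weeks thereafter, as well as at the time of suspected clinical progression". The BOR sort is the only visible place in either document where pseudoprogression appears.

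**The concern.** Pseudoprogression means, in substance, an apparent worsening that is not true progression. Whether the label was right becomes clear only later. If the next evaluable scan is PD, the usual inference is that the earlier scan already showed progression. The visible rules do not return to that earlier scan, so the label keeps its favourable rank in BOR and does not end DOR.

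Two outputs are at stake. In the BOR table some progressors would sit outside the PD row. In the DOR analysis the event would fall on a later scan. Both effects run in the favourable direction only, and a single-arm trial has no comparator in which they could cancel.

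**Working it through.** **Inputs.** Sort order, exclusion rule, ORR numerator and DOR definition: SAP 8.6.2. Scan calendar: Protocol 5.4.9 and 5.4.10, giving Weeks 8, 16, 24, 36, 48. The share of progressors first labelled pseudoprogression, q, is not in the documents. The plan states no figure on this point, so there is none to reproduce.

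**Single sequences.** DOR = week of event minus week of first CR or PR. Recoded means PD is dated at the first pseudoprogression scan.

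| Sequence | BOR, literal | BOR, recoded | DOR, literal | DOR, recoded | Difference |
|---|---|---|---|---|---|
| Pseudoprogression W8, PD W16 | pseudoprogression | PD | none | none | – |
| PR W8, pseudoprogression W16, PD W24 | PR | PR | 24 − 8 = 16 | 16 − 8 = 8 | 8 weeks |
| PR W8 and W16, pseudoprogression W24, PD W36 | PR | PR | 36 − 8 = 28 | 24 − 8 = 16 | 12 weeks |
| PR W8, pseudoprogression W16 and W24, PD W36 | PR | PR | 36 − 8 = 28 | 16 − 8 = 8 | 20 weeks |

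**All sequences.** Five scans with six categories, cut at the first PD, give 5^5 + (1 + 5 + 25 + 125 + 625) = 3,125 + 781 = 3,906 patterns. Recoding pseudoprogression that stands directly before PD has these effects:

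- ORR changes in 0 patterns. Nothing but pseudoprogression lies between the recoded date and the recorded PD, so no CR or PR is lost.
- BOR changes in 10 patterns, always from pseudoprogression to PD and only where there was no CR, PR or SD.
- DOR changes in 116 patterns, all with an earlier CR or PR. It shortens by 8 or 12 weeks for one label, 20 or 24 for two in a row, and 32 for three.
- No pattern has both a BOR and a DOR change.

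These are counts of possible patterns, not of patients. Looking past NE scans to the next evaluable one would add patterns, in the same direction and still without changing ORR.

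**Effect on summary DOR, by assumption.** Assume response at Week 8, exponential true DOR with median m weeks, scheduled scans only, no censoring, no back-dating, and a share q of progressing responders labelled pseudoprogression once before PD. Simulated results:

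| m | q | Median DOR | Mean DOR |
|---|---|---|---|
| 13 | 0 | 16 | 24.0 |
| 13 | 0.1 | 16 | 25.0 |
| 13 | 0.2 | 16 | 26.1 |
| 13 | 0.5 | 28 | 29.3 |
| 13 | 1 | 28 | 34.6 |
| 26 | 0 | 28 | 43.1 |
| 26 | 0.1 | 28 | 44.2 |
| 26 | 0.2 | 40 | 45.3 |
| 26 | 0.5 | 40 | 48.7 |
| 26 | 1 | 40 | 54.3 |

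The median moves in steps because events fall on scan dates, and the step can be located exactly:

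- m = 13: the share with recorded DOR of at most 16 weeks is (1 − 2^(−8/13)) + (2^(−8/13) − 2^(−16/13))(1 − q) = 0.347 + 0.227(1 − q). This is at least 0.5 while q ≤ 1 − 0.153/0.227 = 0.33.
- m = 26: the share with recorded DOR of at most 28 weeks is (1 − 2^(−16/26)) + (2^(−16/26) − 2^(−28/26))(1 − q) = 0.347 + 0.179(1 − q). This is at least 0.5 while q ≤ 1 − 0.153/0.179 = 0.145.

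Below those shares the median does not move; above them it rises by 12 weeks.

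**The case against.** The strongest objection is that the rule may exist out of sight. SAP Section 7, including 7.1 Derived variables, is listed in the contents but its text is not in the public copy. Parts of Protocol 5.4.9 and 5.4.10 are blacked out, and imaging detail is deferred to an Imaging Manual. A reader might infer that the SAP never reclassifies the label; the documents do not support that. What stands is narrower: the visible BOR and DOR text and Tables 1 and 3 contain no such rule and point to none.

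Other objections also carry weight:

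- The IRC sets the progression date, and nothing forbids it from back-dating. The DOR effect is therefore conditional.
- A subject may have a true pseudoprogression and then separate, later PD. A recode would date that PD too early.
- Protocol 5.4.10 says what modified Lugano refers to. It does not say this is the only modification, so the category cannot be called foreign to the protocol criteria.
- The DOR endpoint in SAP 4.2 rests on IRC assessment. A worry about unblinded labelling reaches only the additional Investigator DOR.
- BOR is shown as a frequency table, all response assessments are listed, and swimmer plots are drawn. A reader could see the pseudoprogression row and trace the subjects.

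These limit the size of the concern. They do not supply the missing rule, and a listing does not correct the Kaplan-Meier estimate.

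**Conclusion.** The concern holds as a gap in the visible rules with a one-directional consequence. Followed literally, they give a BOR of pseudoprogression to a subject who progressed at the next evaluable scan without ever reaching SD or better. For a different set of subjects, responders, they date the DOR event 8 or 12 weeks later per label on scheduled scans. The delay is shorter if suspected clinical progression prompts an earlier scan, and longer if the label repeats. It disappears if the evaluator back-dates.

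Three stronger readings are tempting and unsupported. One is that the same subject suffers both effects: a BOR of pseudoprogression means no response and so no DOR, and a responder's BOR stays CR or PR. Another is that reported DOR is inflated by a known amount: this depends on q, which the documents do not give, and under the assumptions above a 10% share adds about 1 week to the mean and leaves the median where it is. The third is that the main secondary endpoint is compromised: DOR is one of several secondary endpoints and the documents do not rank it first.

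The primary ORR and its exact test are unaffected for the subjects described. The gap is worth closing before database lock, but it does not threaten the primary result.

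**What to change.** Define pseudoprogression in SAP 8.6.2, including who may assign it and under which criteria. Then add there, and in the notes to Tables 1 and 3, text to this effect:

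*For BOR and DOR, one or more consecutive pseudoprogression assessments whose next evaluable assessment, by the same evaluator and modality, is PD are recoded as PD on the date of the first of them. The label stands only if a later assessment shows SD or better.*

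State also how pseudoprogression followed by death, or by no further evaluable scan, is handled. As Tables 1 and 3 read now, a responder who dies has the event at death. In Table 1 a responder with no later scan is censored at the last disease assessment, which is the pseudoprogression scan itself. Say whether that stands and which BOR category such subjects receive. Report DOR without the recode as a sensitivity analysis. If SAP Section 7 or the Imaging Manual already holds a rule, a cross-reference from 8.6.2 and the tables may be enough.

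The cost is a short SAP addition and some programming, with no new data. DOR may come out slightly shorter and the PD row slightly larger. A true pseudoprogression followed by separate later PD would be dated early, and the sensitivity analysis shows how much that matters.

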2 STUDY OBJECTIVES AND ENDPOINTS

This is a Phase 2 study to evaluate the antitumor activity and safety of AFM13 given as monotherapy in subjects with CD30-positive T-cell lymphoma. The study objectives and their respective endpoints for assessment are described in [Table 2](#).

Table 2: Study Objectives and Endpoints

Objective	Endpoint (Assessment)

PRIMARY:
 
 To assess the antitumor activity of AFM13 by an IRC-PET-CT based ORR 	
 ORR (CR + PR) as confirmed by an IRC as assessed by the modified Lugano Classification (Cheson, 2014) for Cohorts A and B (PTCL) based on PET-CT and after at least 8 weeks from the first assessment as assessed by Olsen Criteria (Olsen, 2011) for Cohort C (TMF) [REDACTED]

SECONDARY:
 
 To assess the antitumor activity of AFM13 by IRC-confirmed CR and PR rates and CT scan-based ORR To assess the antitumor activity of AFM13 by Investigator-assessed ORR (defined as ORR-2) To assess the DOR to AFM13 To assess the safety and tolerability of AFM13 To assess the PK of AFM13 	
 CR rate, PR rate, and CT-based ORR as confirmed by an IRC as assessed by the modified Lugano Classification (Cheson, 2014) for Cohorts A and B (PTCL) and after at least 8 weeks from the first assessment by Olsen Criteria (Olsen, 2011) for Cohort C (TMF) [REDACTED] ORR-2 confirmed by Investigator assessment as assessed by the modified Lugano Classification (Cheson, 2014) for Cohorts A and B (PTCL) and after at least 8 weeks from the first assessment by Olsen Criteria (Olsen, 2011) for Cohort C (TMF) [REDACTED] DOR as assessed by the modified Lugano Classification (Cheson, 2014) for Cohorts A and B (PTCL) and after at least 8 weeks from the first assessment by Olsen Criteria (Olsen, 2011) for Cohort C (TMF) based on IRC assessment [REDACTED] Number and frequency of treatment-related AEs Assessment of non-compartmental PK parameters including C_{max}, AUC, V_{ss}, $t_{1/2}$

The estimand corresponding to the primary objective consists of:

- Population: defined through appropriate inclusion/exclusion criteria to reflect the targeted subject population for approval.

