- Variable: Response assessment from the first assessment as assessed by the modified Lugano Classification ([Cheson, 2014](#)) for Cohorts A and B (PTCL) and after at least 8 weeks from the first assessment as assessed by Olsen Criteria ([Olsen, 2011](#)) for Cohort C (TMF) [REDACTED]
- Intercurrent event strategy will follow the treatment policy strategy: subjects non-evaluable for efficacy will not be replaced.

Subjects with missing post-baseline response assessment will be classified as non-responders regardless of the reason.

[REDACTED]

- Population-level summary: Percentage of subjects achieving an overall response.

Estimator: Best objective response rate assessed via positron emission tomography (PET)-computed tomography (CT) and evaluated by independent central review, for all subjects in the full analysis set (FAS).

Sensitivity estimand: [REDACTED]

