4 STUDY ENDPOINTS

4.1 Primary efficacy endpoint

The primary efficacy endpoint of this study is:

- ORR (CR + PR) as confirmed by an IRC as assessed by the modified Lugano Classification (Cheson, 2014) for Cohorts A and B (PTCL) based on PET-CT and after at least 8 weeks from the first assessment as assessed by Olsen Criteria (Olsen, 2011) for Cohort C (TMF).

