4.2 Secondary efficacy endpoints

The secondary efficacy endpoints of this study are:

- CR rate, PR rate, and CT-based ORR as confirmed by an IRC as assessed by the modified Lugano Classification (Cheson, 2014) for Cohorts A and B (PTCL) based on CT and after at least 8 weeks from the first assessment by Olsen Criteria (Olsen, 2011) for Cohort C (TMF).
- ORR-2 confirmed by Investigator assessment as assessed by the modified Lugano Classification (Cheson, 2014) for Cohorts A and B (PTCL) and after at least 8 weeks from the first assessment by Olsen Criteria (Olsen, 2011) for Cohort C (TMF).
- DOR as assessed by the modified Lugano Classification (Cheson, 2014) for Cohorts A and B (PTCL) and after at least 8 weeks from the first assessment by Olsen Criteria (Olsen, 2011) for Cohort C (TMF) based on IRC assessment.
- Assessment of non-compartmental PK parameters including C_{max} , AUC, volume of distribution at steady state (V_{ss}), half-life ($t_{1/2}$).
- Incidence of subjects who develop anti-drug antibodies (ADA) during treatment in blood and their neutralizing potential.
- QOL as measured by European Quality of Life 5-Dimensional (EQ-5D) for Cohorts A and B, and by Skindex-29 for Cohort C.

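### Cohort C endpoints carry an 8-week condition that the SAP rule behind the ORR test does not apply; if the undefined first assessment is post-baseline, the tested ORR is not the stated endpoint

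*SAP*

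**What the plan says.** **Endpoint side.** Protocol Section 2, Table 2 gives the primary endpoint as IRC-confirmed ORR, for Cohorts A and B "based on PET-CT and after at least 8 weeks from the first assessment as assessed by" the Olsen criteria for Cohort C. SAP 4.1 repeats the Cohort C condition: "and after at least 8 weeks from the first assessment as assessed by" those criteria. SAP 4.2 attaches it ("after at least 8 weeks from the first assessment by" Olsen) to the CR and PR rates, to ORR-2 and to DOR. The estimand variable (Protocol 2.1) carries it for Cohort C, whereas for Cohorts A and B it reads "Response assessment from the first assessment as assessed by the modified Lugano Classification".

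**Analysis side.** SAP 8.6.2 takes the best response from the start of treatment, discards responses after progression, new anti-cancer therapy or transplant, and says that "best response assignment will depend on the achievement of the measurement criteria (confirmation is not required". ORR is then the proportion with CR or PR. The rule is written for all cohorts. The one cohort-specific sentence, "For Cohorts A and B, BOR is derived for radiographic (using only CT-based responses) and metabolic responses", only separates two imaging bases. The exact binomial test is used for what the SAP words as "analysed the ORR of the Cohorts A and C at the final analysis only", with a null of 5% for Cohort C.

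Two protocol statements also omit the 8-week condition: the primary analysis in Section 8.5.1, and the estimator in Section 2.1, given as "Best objective response rate assessed via positron emission tomography (PET)-computed tomography (CT) and evaluated by independent central review".

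**The concern.** Two stated rules for the same primary result differ in visible text. The endpoint has a timing condition for Cohort C, and the derivation has none. Whether this matters turns on what *first assessment* means. If the anchor is post-baseline, a short-lived early response counts in the tested ORR but not in the endpoint as worded. The p-value, the confidence interval and the CR and PR rates would then describe a different quantity from the one named as primary.

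Cohort C is one of only two cohorts with a formal test, and it has about 20 subjects, so one or two reclassified subjects can matter. The planned listings and swimmer plots would allow a recount, but they would not say which count is the primary result.

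**Working it through.** **1. What each reading does.** Protocol 5.4.9 schedules assessments at screening, then every 8 weeks three times, then every 12 weeks. Take two illustrative subjects:

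| Rule | PR wk 8, PD wk 16 | SD wk 8, PR wk 16, PD wk 24 |
|---|---|---|
| SAP 8.6.2 as written | responder | responder |
| Endpoint, anchor = baseline | responder | responder |
| Endpoint, anchor = first post-baseline assessment | not a responder | responder |
| Endpoint, anchor = first response, to be seen again | not a responder | not a responder |

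Under the baseline anchor, the first scheduled scan already qualifies. Only early or unscheduled scans could differ.

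**2. Where the test turns.** Inputs: null rate 0.05 (SAP 8.6.2) and n = 20, maximum 22 (Protocol synopsis). The p-value for k responders is P(X ≥ k), with X ~ Bin(n, 0.05). For n = 20:

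- P(0) + P(1) + P(2) = 0.35849 + 0.37735 + 0.18868 = 0.92452, so P(X ≥ 3) = 0.0755.
- Adding P(3) = 0.05958 gives 0.98410, so P(X ≥ 4) = 0.0159.

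| n | 3 responders: p (Clopper-Pearson 95% CI) | 4 responders: p (95% CI) |
|---|---|---|
| 20 | 0.0755 (3.2–37.9%) | 0.0159 (5.7–43.7%) |
| 21 | 0.0849 (3.0–36.3%) | 0.0189 (5.4–41.9%) |
| 22 | 0.0948 (2.9–34.9%) | 0.0222 (5.2–40.3%) |

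The level of this one-sided test is not visible; SAP 8.1 gives 0.05 two-sided as the default. At one-sided 0.025 or 0.05 the cut is 4 responders for every n, and the lower confidence limit passes 5% at the same step. The cut is therefore inferred, not quoted. The sample size section (Protocol 8.8.1) is redacted, so there is no planned figure to reproduce, and any stage-one rule is ignored.

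**3. Chance that the two rules give different test results.** Let p be the true any-time ORR and q the share of any-time responders who also meet the 8-week condition, independently between subjects. Neither is in the documents, so both are shown as ranges. The endpoint count cannot exceed the any-time count, so the chance of discordance is

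P(X ≥ 4 at rate p) − P(X ≥ 4 at rate p·q).

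Example, n = 20, p = 0.20, q = 0.8: 0.589 at rate 0.20 minus 0.401 at rate 0.16 gives 0.188, about 19%.

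| q | n | p = 10% | 15% | 20% | 25% | 30% |
|---|---|---|---|---|---|---|
| 0.9 | 20 | 3% | 7% | 9% | 8% | 6% |
| 0.9 | 22 | 4% | 8% | 9% | 7% | 5% |
| 0.8 | 20 | 6% | 14% | 19% | 19% | 15% |
| 0.8 | 22 | 8% | 16% | 19% | 17% | 12% |
| 0.5 | 20 | 12% | 29% | 46% | 54% | 54% |
| 0.5 | 22 | 15% | 35% | 50% | 54% | 51% |

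Between the columns, the q = 0.5 row peaks at 55% (n = 20, p near 27%). Under the baseline anchor q is close to 1 and the difference is close to 0.

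**The case against.** The strongest reply is that the consequence depends on text that cannot be read. Redactions follow the clause in Protocol Table 2 and in the estimand. Parts of Protocol 5.4.9 and 5.4.10 are redacted. SAP Section 7, which includes derived variables, and SAP Section 9, where departures from the protocol would be declared, are not shown. A definition or a declared change may stand there. The baseline reading is also viable, because screening is the first scheduled disease assessment. The estimand's contrast between cohorts, together with Protocol 5.4.10 tying response to post-dose assessments, leans towards a post-baseline anchor. But that is one sentence, and it may be loose drafting. All of this stands. Even so, a hidden definition of the term would not by itself put the condition into the 8.6.2 rule, and that rule refers to none.

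It is also true that SAP 8.6.2, Protocol 8.5.1 and the estimator agree with each other, so the analysis is pre-specified. The problem is what the count represents.

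A reader might infer four stronger things, which the documents do not support:

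- *That Cohort C has no response rule.* The general best overall response rule covers it. The sentence on Cohorts A and B only splits CT from PET.
- *That the tested ORR is certainly the wrong quantity.* Under the baseline anchor the two nearly coincide.
- *That IRC-confirmed means a repeat scan.* It can simply mean reviewed by the IRC. The point rests on the 8-week clause alone.
- *That the chance of exactly 4 responders (9 to 22% over the same true rates) is the chance of a changed result.* It is not, because the answer also depends on q.

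**Conclusion.** The mismatch between the Cohort C endpoint wording and the SAP 8.6.2 derivation is established in visible text. Its consequence is conditional on the undefined anchor: close to nil if it is baseline, and a tested ORR that is not the stated endpoint if it is the first post-baseline assessment or the first response.

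In the second case the sizes in the working apply: roughly 3 to 9%, 6 to 19% or 12 to 55% for q of 0.9, 0.8 or 0.5. They rest on a single-stage test, an inferred cut of 4 responders and assumed values of p and q. It should be fixed, because it concerns the primary endpoint of a formally tested cohort and the correction is cheap before database lock.

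**What to change.** Before database lock, state in SAP 8.6.2 what *first assessment* is for Cohort C. If a definition already exists in text not visible here, repeat it there. Then apply the endpoint's condition to the Cohort C best overall response, CR and PR rates, ORR, confidence interval and exact test. Say whether the response must still be present at the later assessment. Say also how responders without a later assessment are classed, for example those moved to transplant, whom SAP 3.1 counts as having completed the study. Show the count under the present 8.6.2 rule as a supportive row.

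Reconcile Cohort C DOR as well. SAP 4.2 and Protocol Table 2 put the same clause on it, whereas SAP 8.6.2 starts it at the first PR or CR. State the start date explicitly.

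The alternative is to remove the clause from the endpoints and the estimand. That changes the protocol's primary endpoint, so it is an amendment and should be documented as one (Protocol Section 10), with a justification.

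The first route costs SAP wording and a derivation flag, with no extra scans or data. Its downside is that the Cohort C ORR may be lower. Cohorts A and B stay as they are.
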